#### **5.6 Blinding**

As this is a double-blind study, blinding of the drug contents from the subjects, investigator, and other study personnel at each site is necessary. The subject will be assigned with an identification number at Visit 2 which will remain with the subject throughout the study.

A code-break document including the randomization code information will be retained by each site and can be opened, revealing the randomization information, for emergency purposes only. The investigator should note that the occurrence of a SAE should not routinely precipitate immediate unblinding. An attempt to contact the Sponsor must be made prior to unblinding. If unblinding occurs, the study medication for the subject must be discontinued; a written explanation on the relevant form must be prepared immediately.

#### **5.7 Prior and Concomitant Treatments**

All the subjects will be instructed to continue their current diabetes medications and all other prescribed drugs. All prior (2 months prior to Screening) and concomitant medications must be entered into the electronic case report form (eCRF), including the name of the drug or treatment, dose, route of administration, date and time of the treatment, and indication. In the event that prior or concomitant medication is administered, the investigator must access the subject's eligibility of continuing the participation in the study.

The following medications are not allowed to be taken by subjects enrolled in this study during the trial:

- Psychoactive agents such as monoamine oxidase inhibitors and antidepressive agents (e.g., lithium, Prozac, Zoloft, Serzone, Paxil, Effexor)
- Any other medications that may pose harm to the subject

- Any investigational drug (including placebo)

## **5.8 Subject Education on Hypoglycemia/Hyperglycemia and its Management**

All subjects will be instructed in life style modification and asked to maintain a stable diet and daily exercise routine and to keep a daily record of their blood glucose level before breakfast and 2 hours after dinner. Hypo- or hyperglycemia are of particular concern and if either occurs, it will be handled in a standard fashion as outlined in Section 9.5, Procedures for Managing Hypoglycemia and Hyperglycemia.

Although Cyclo-Z treatment alone does not cause hypoglycemia in human as demonstrated in the prior informal study, it may potentially lead to hypoglycemia when interacting with other anti-diabetic drugs. The interaction between Cyclo-Z and other oral anti-diabetic agents or obesity medications are not known at this time. However, some anti-diabetic agents such as insulin injection, sulfonyl derivatives or other insulin secretion stimulating agents may cause hypoglycemia regardless of Cyclo-Z treatment. Improved insulin resistance during the study requires reduction in the use of other insulin and insulin secretagogues. Thus, subjects' blood glucose levels should be closely monitored to detect hypoglycemia in order for the use of other anti-diabetic agents to be appropriately reduced. For the purpose of record keeping and maintaining subject's health, all subjects will be provided with their own glucometer to measure their blood glucose levels. If there are subjects with a possibility of developing acute hypoglycemia while using their current hypoglycemic agents concomitantly with Cyclo-Z, they will be instructed to carry commercial glucose tablets with them to take when feeling dizzy and weak. While taking Cyclo-Z, an improvement in insulin sensitivity or symptoms of hypoglycemia will not develop acutely. Furthermore, 2-week periodical examinations and subjects' daily blood glucose measurements will keep their glucose levels on track and help prevent them from experiencing possible hypoglycemic episodes.

At the same time, hyperglycemia will be well maintained by examining subjects bi-weekly. Taking Cyclo-Z may increase fasting blood glucose initially for 2 months due to the reduction in pancreatic insulin secretion, which could occur with improved insulin sensitivity. Subjects will be instructed to monitor for increased thirst, urination and blurry vision, but subjects will also be advised that the best method for detecting hyperglycemia is by measuring blood glucose level.

## **5.9 Medication Accountability and Treatment Compliance**

Subjects will return all unused study medications with the diary at Visits 3, 4, 5, 6, 7, and 8 (Weeks 2, 4, 6, 8, 10, and 12) or at Early Termination Visit. The returned medications and diaries will be reviewed with the subject to evaluate the medication accountability and treatment compliance. If a subject misses 3 or more doses out of total 2-week doses (i.e., 14 doses), the site should contact the Sponsor for the discussion of potential early termination.

All study medication supplies should be accounted for at the termination of the study and a written explanation provided for discrepancies. All unused study medication supplies and packaging materials are

to be inventoried and returned to the Sponsor by the investigator. The investigator is not permitted to return or destroy unused clinical drug supplies or packaging materials unless authorized by the Sponsor.

The medication doses for the diabetes treatment should not be changed during the 3-month treatment period.

## 6. Study Procedures

Refer to the Schedule of Assessments for an outline of study specific procedures/assessments required at each visit. Additional procedures as part of standard of care may be performed whenever the investigator determines it is necessary.

The study duration for each subject may be up to 16 weeks. This includes a 2-week screening period, a 12-week treatment period from randomization to the last treatment visit, and a 2-week safety follow up period. All visits from Visit 2 should occur within 6 days (i.e.,  $\pm 3$  days) from the initial schedule for Visits 3 to 8 and within 7 days (i.e., + 7 days) for Visit 9, respectively.

Each subject will be required to visit the clinical site, in a fasted state, before breakfast approximately 9 times over a period of 16 weeks starting at Screening. All missed visits and any procedures that are not performed per protocol must be documented in the source documents and the appropriate CRF.

### 6.1 Screening Period

A screening visit will occur at least 2 weeks prior to the randomization.

A signed and dated Institutional Review Board (IRB) approved Informed Consent Form must be obtained before any study-specific procedures are performed. Once written informed consent has been obtained, the following screening procedures and assessments must be performed to determine eligibility and document adherence to the preliminary inclusion/exclusion criteria:

- Record demographic data (i.e., date of birth, race, and height).
- Record relevant medical history including diabetic history.
- Record details of previous medications.
- Perform a physical examination.
- Measure vital signs (sitting blood pressure, pulse, breathing, and temperature) and weight.
- Measure 12-lead ECG.
- Collect blood samples for hematology, serum chemistry, HbA1c, and pregnancy test (serum hCG).
- Dispense daily log with blood glucose monitoring devices to record daily blood glucose values (fasting before breakfast and two hours after dinner) and study medication adherence (See Appendix 2).

### 6.2 Treatment Period

#### 6.2.1 Visit 2 (Week 0): Baseline

Visit 2 will occur after the completion of 2-week assessment (+7 days). During this visit, the following procedures and assessments must be performed:

- Measure vital signs (sitting blood pressure, pulse, breathing, and temperature) and weight.
- Perform a physical examination.

- Collect daily logs and blood glucose monitoring devices and review daily logs with the subject.
- Record any changes in concomitant medications.
- Record an adverse event, if applicable.
- Assess hypoglycemic and hyperglycemic episodes (See Appendix 4).
- Confirm the inclusion and exclusion criteria.
- Randomize the subject
- Conduct the ADDQoL Questionnaire (See Appendix 3).
- Perform the OGTT (See Appendix 1)
- Measure waist circumference.
- Collect blood samples for hematology, serum chemistry, HbA1c, FPG, and thyroid function test (TSH, T3, and T4).
- Collect blood samples\* for zinc, insulin, adiponectin, C-peptide, leptin, and glucagon.
- Collect urine samples for glucose, microalbumin, copper, and zinc.
- Dispense study medications to the subject with detailed instructions.
- Dispense daily log with blood glucose monitoring devices to record daily blood glucose values (fasting before breakfast and two hours after dinner) and study medication adherence (See Appendix 2).

\*If residual plasma and/or serum are available, CHP levels may be measured.

#### 6.2.2 Visits 3, 5, and 7 (Weeks 2, 6, and 10)

Each study visit will occur 2 weeks ( $\pm$  3 days) after the previous visit. During each visit, the following procedures and assessments must be performed:

- Measure vital signs (sitting blood pressure, pulse, breathing, and temperature) and weight.
- Review adverse events and concomitant medications.
- Assess hypoglycemic and hyperglycemic episodes (See Appendix 4).
- Collect daily logs and blood glucose monitoring devices and review daily logs with the subject.
- Collect unused study medications and review the medication accountability with the subject.
- Dispense study medications to the subject.
- Dispense daily log with blood glucose monitoring devices to record daily blood glucose values (fasting before breakfast and two hours after dinner) and study medication adherence (See Appendix 2).

#### 6.2.3 Visits 4 and 6 (Weeks 4 and 8)

Each study visit will occur 2 weeks ( $\pm$  3 days) after the previous visit. During each visit, the following procedures and assessments must be performed:

- Collect daily logs and blood glucose monitoring devices and review daily logs with the subject.
- Collect unused study medications and review the medication accountability with the subject.
- Review adverse events and concomitant medications.
- Assess hypoglycemic and hyperglycemic episodes (See Appendix 4).
- Measure vital signs (sitting blood pressure, pulse, breathing, and temperature) and weight.

- Perform a physical examination.
- Measure waist circumference.
- Collect blood samples for hematology, serum chemistry, HbA1c, and FPG.
- Collect blood samples\* for zinc, insulin, adiponectin, C-peptide, leptin, and glucagon.
- Collect urine samples for glucose, microalbumin, copper, and zinc.
- Dispense study medications to the subject.
- Dispense daily log with blood glucose monitoring devices to record daily blood glucose values (fasting before breakfast and two hours after dinner) and study medication adherence (See Appendix 2).

\*If residual plasma and/or serum are available, CHP levels may be measured.

#### 6.2.4 Visit 8 (Week 12) or Early Termination Visit

This study visit will occur 2 weeks ( $\pm$  3 days) after Visit 7 or when the subject is early terminated due to any reason. During this visit, the following procedures and assessments must be performed:

- Conduct the ADDQoL Questionnaire (See Appendix 3).
- Collect daily logs and blood glucose monitoring devices and review daily logs with the subject.
- Collect unused study medications and review the medication accountability with the subject.
- Perform the OGTT (See Appendix 1)
- Assess hypoglycemic and hyperglycemic episodes (See Appendix 4).
- Review adverse events and concomitant medications.
- Measure vital signs (sitting blood pressure, pulse, breathing, and temperature) and weight.
- Perform a physical examination.
- Measure waist circumference.
- Measure 12-lead ECG.
- Collect blood samples for hematology, serum chemistry, HbA1c, FPG, thyroid function test (TSH, T3, and T4), and pregnancy test (serum hCG).
- Collect blood samples\* for zinc, insulin, adiponectin, C-peptide, leptin, and glucagon.
- Collect urine samples for glucose, microalbumin, copper, and zinc.

\*If residual plasma and/or serum are available, CHP levels may be measured.

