### Schedule of Assessments

*Note: A subject needs to visit the clinical site before breakfast for all study visits except the safety follow-up visit.*

Study Visits 	Screening	Treatment Period							Follow-up
	V1	V2	V3	V4	V5	V6	V7	V8	V9
	Screen (Wk -2)	Baseline (Wk 0)	Wk 2	Wk 4	Wk 6	Wk 8	Wk 10	Wk 12	Wk 14
Informed Consent	X								
Inclusion/Exclusion Criteria	X	X							
Demographic (including height)	X								
Medical/Medication History	X								
Physical Examination	X	X		X		X		X	
Vital Signs and Body Weight	X	X	X	X	X	X	X	X	X
12-lead ECG	X							X	
Blood Sampling for serum chemistry, hematology, FPG, HbA1c, hCG, TSH, T3, and T4 	X	X		X		X		X	
Blood Sampling for zinc, insulin, adiponectin, C-peptide, leptin, glucagon, (CHP in a subset of subjects  )		X		X		X		X	
Urine Sampling for glucose, microalbumin, copper, and zinc		X		X		X		X	
Dispense and Review Daily Log	X	X	X	X	X	X	X	X	
Dispense and Review Medications		X	X	X	X	X	X	X	
Waist Circumference		X		X		X		X	
OGTT 		X						X	
ADDQoL Questionnaire		X						X	
Review of Adverse Event and Concomitant Medication 		X	X	X	X	X	X	X	X

- 1) Visits 3 to 8 have ±3 day visit window and Visit 9 has +7 day visit window.
- 2) Serum chemistry, hematology: Weeks -2, 0, 4, 8, and 12  
HbA1c: Weeks -2, 0, 4, 8, and 12  
FPG: Weeks 0, 4, 8, and 12  
TSH, T3, T4: Weeks 0 and 12  
Serum hCG (pregnancy): Weeks -2 and 12
- 3) CHP levels may be analyzed in a subset of subjects if residual serum and/or plasma samples are available after completion of protocol-required tests.
- 4) See Appendix 1.
- 5) Assess hypoglycemic & hyperglycemic episodes at Visits 2 to 8 only.

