### **4.3 Subject Withdrawal**

Any subject is free to withdraw from participation in the study at any time, for any reason, specified or unspecified, and without prejudice to further treatment. The criteria for enrollment are to be followed explicitly. If a subject who does not meet enrollment criteria is inadvertently enrolled, that subject should be withdrawn from the study and the Sponsor/contract research organization (CRO) must be contacted. An exception may be granted in rare circumstances where there is a compelling reason to allow the subject to continue. In these rare cases, the investigator must obtain documented approval from the Sponsor or Sponsor designee to allow the subject to continue in the study.

In addition, subjects will be withdrawn from study drug and from the study in the following circumstances:

- The investigator decides that the subject should be withdrawn. If this decision is made because of an intolerable AE or a clinically significant laboratory value, if the dose of study drug has not been administered, it will be withheld and appropriate measures are to be taken. The Sponsor or Sponsor designee is to be notified immediately.
- The subject is unwilling to continue in the study.
- The subject is not compliant with the protocol.
- The investigator or the Sponsor, for any reason, stops the study.

If a subject prematurely withdraws from the study, every effort must be made to have the subject return to the clinical site for a premature termination visit. In all cases, the reason for withdrawal must be recorded in the Electronic Case Report Form (eCRF) and in the subject's medical records.

Contact will be maintained with subjects who are removed due to an AE until it has been resolved or stabilized, and the information will be documented in the eCRF and in the subject's medical records.

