If a subject experiences an increase in FPG level of >270 mg/dl from baseline to Week 6 or >240 mg/dl from Week 6 to 12, the subject will be instructed to take his/her own hypoglycemic agent. It is expected that glucose levels can be controlled in most diabetic subjects by these treatments. If the subject's blood glucose levels do not decrease to an acceptable level (<240 mg/dl) after 2 weeks, the subject will be referred to a diabetologist and will be terminated from the study. The study physician will continue to evaluate and treat the subject as needed until healthcare is turned over to the diabetologist.

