## **12. APPENDICES**

### **Appendix 1: Oral Glucose Tolerance Test (OGTT)**

Subjects will be advised to maintain similar exercise and eating habits 3 days prior to the OGTT. Each subject will be instructed not to take his or her usual oral medications or insulin injection and food at least 12 hours before coming to the clinical site between 7:00 am and 8:30 am for an OGTT. Each subject will be allowed to drink only water during the 12-hour fasting period prior to the OGTT and advised not to consume any food. Initial blood will be drawn (15 min prior to OGTT) for serum chemical analysis. The subject will then consume a glucose solution (75 g), followed by one drop of blood drawn for glucose measurements with a glucometer at 0, 0.5, 1.0, 1.5, 2.0, 2.5 and 3 h in the clinical site.

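### Protocol 6.2.4 requires an OGTT at every early termination, with no waiver for a subject terminated under 9.5 for uncontrolled hyperglycemia

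*Protocol*

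**What the plan says.** Protocol 6.2.4 covers two occasions with one list: Visit 8, and the visit that takes place "when the subject is early terminated due to any reason. During this visit, the following procedures and assessments must be performed". The OGTT is on the list and no condition is attached to it. Section 4.3 presses for attendance: "every effort must be made to have the subject return to the clinical site for a premature termination visit".

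Protocol 9.5 sets the hyperglycemia rule. A subject who crosses an FPG threshold (270 mg/dl up to Week 6, 240 mg/dl from Week 6 to Week 12) is told to take his or her own hypoglycemic agent. If glucose has not come below 240 mg/dl "after 2 weeks, the subject will be referred to a diabetologist and will be terminated from the study". The section goes on: "The study physician will continue to evaluate and treat the subject as needed until healthcare is turned over to the diabetologist".

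Appendix 1 describes the test, and note 4 to the schedule in SAP 3.1.2 repeats it. On preparation: "Each subject will be instructed not to take his or her usual oral medications or insulin injection and food at least 12 hours" before attending. On the load: "The subject will then consume a glucose solution (75 g), followed by one drop of blood drawn for glucose measurements with a glucometer". Readings run to 3 hours. Neither text gives a glucose level above which the test is not done.

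**The concern.** Followed exactly, the three sections work against each other for one kind of subject. Section 9.5 treats high glucose by having the subject take glucose-lowering drugs, and terminates the subject if that fails. The visit triggered by the termination then has the same subject leave those drugs off for at least 12 hours and take a glucose load.

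Fasting is not the added burden, because the schedule already says: "A subject needs to visit the clinical site before breakfast for all study visits except the safety follow-up visit". What the OGTT adds is the drug omission and the 75 g drink.

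At stake is one foreseeable and avoidable exposure per such subject. The co-primary endpoints, HbA1c and body weight, do not use the test.

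**Working it through.** **1. Does a 9.5 termination trigger the OGTT?** Section 9.5 ends participation. Section 6.2.4 applies to termination for any reason and makes its list mandatory. The list includes the OGTT, and Appendix 1 supplies the drug omission and the load. Each step is explicit, so the answer is yes.

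**2. Does any text lift the requirement?** The relevant clauses are:

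- Protocol 6: "any procedures that are not performed per protocol must be documented in the source documents and the appropriate CRF". This covers a test that was not done; it does not say when to omit it.
- Protocol 7.2: the investigator may depart from the protocol to remove an immediate hazard, with an explanation afterwards. The OGTT is not named.
- Protocol 9.5: the investigator follows the diabetes association's standard of care, and the study physician keeps treating the subject until handover. The OGTT is not named.
- Appendix 1 and SAP 3.1.2: no ceiling, stopping rule or exemption.

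The clauses permit an omission. None waives the test.

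**3. What would a waiver remove from the analysis?** The OGTT is scheduled only at Weeks 0 and 12. SAP 9.4 maps an early termination visit to the closest scheduled visit.

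- Observed-data analysis at Week 12: affected only if the termination visit maps to Week 12.
- Per Protocol Set: unaffected, since SAP 7.3 excludes subjects who terminated early.
- LOCF sensitivity analysis: affected. The subject stays in the Efficacy Analysis Set through other post-baseline efficacy data, such as weight, but has no post-baseline OGTT. SAP 9.3.3 then carries the baseline value forward, so the change is zero.
- TAFGC: no LOCF analysis is planned. Any value from that visit is lost.

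**4. Size of the LOCF effect.** The documents give no OGTT changes, so these inputs are assumptions:

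- n = 16 per arm (the planned arm size), all in the analysis
- D = true change in 2-hour glucose in the waived subject, +50 to +150 mg/dl
- m = mean change in the other 15

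Arm mean with the test done = (15m + D)/16.

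Arm mean with the test waived = (15m + 0)/16.

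Difference = D/16, whatever the value of m.

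- D = +50: 50/16 = 3.1 mg/dl
- D = +150: 150/16 = 9.4 mg/dl

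Each waiver therefore lowers its arm's LOCF mean change by about 3 to 9 mg/dl and so hides a worsening. SAP 13 also contains an incomplete sentence that could be read as requiring a post-baseline value, which would drop the subject instead. Section 9.3.3 is explicit, so it is used here.

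**5. Would waivers be balanced across arms?** Perhaps not. Protocol 5.8 says that Cyclo-Z may raise fasting glucose during the first 2 months. Exits for hyperglycemia, and so waivers, may then fall mainly in the active arms. With one waiver in an active arm and none on placebo, the LOCF contrast moves by the full D/16 in favour of Cyclo-Z.

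**6. Whom does a termination waiver miss?** A subject who crosses the threshold less than 2 weeks before Visit 8 is not yet due for termination, so the scheduled OGTT goes ahead.

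**The case against.** The strongest reply is that existing safeguards are enough. Standard of care is stated as something the investigator will follow, the study physician stays responsible for this same subject, and an immediate hazard justifies a departure without prior approval. There is also a natural decision point. The drug omission has to be instructed at least 12 hours ahead, so an OGTT done as Appendix 1 requires cannot simply follow a termination decision made at an ordinary fasted visit.

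This stands in part. It defeats a stronger reading that a reader might infer, namely that the sections contradict each other or that a site is compelled to give the load whatever the glucose level. The documents do not support that, because a physician has room to skip the test. What remains is that each site must think of it and then record a departure from a mandatory item, in a situation that the protocol itself foresees.

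A second reply is that the harm is not in the documents. That is correct. Neither document describes the risk of an OGTT at these glucose levels; that the test is better avoided is clinical judgement.

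A third is that the group is tiny. This is also likely. The 9.5 trigger is worded as an increase in FPG. If that means a rise of more than 270 or 240 mg/dl, and not a level above those figures, such exits would be rarer still.

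**Conclusion.** The point holds as a minor safety improvement. The missing waiver is certain from the text. The benefit of adding one rests on clinical judgement and applies to a group of unknown, probably very small, size. The documents give no rate of 9.5 exits, so no count is claimed.

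The statistical cost is confined mainly to a sensitivity analysis of a secondary endpoint. The figure of 3 to 9 mg/dl per waived subject depends wholly on the assumed changes and the arm size of 16; it shows scale and does not predict a result.

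A reader might also infer that a glucose limit on the 0-hour reading would solve the whole problem, including the subject close to Visit 8. Appendix 1 as written does not support this. It places the glucometer readings, including 0 hours, after the drink, and the only draw before it is for serum chemistry.

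**What to change.** 1. Add to Protocol 6.2.4: *The OGTT and the 12-hour omission of oral medications and insulin are not done in a subject terminated for hyperglycemia under Section 9.5.* Keep every other assessment at that visit, including HbA1c, FPG, weight, safety laboratory tests and adverse event review.
2. Report the number of waived OGTTs by arm beside the reasons for withdrawal (SAP 10.2), and state how these subjects were handled in the OGTT LOCF analysis.

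The cost is one protocol sentence and one reporting note, plus the loss of some high OGTT values, possibly more from active arms than from placebo. The count by arm lets a reader see whether the LOCF result could be flattered.

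The waiver leaves the subject who crosses the threshold shortly before Visit 8 uncovered. A pre-load limit could be considered for that case only if Appendix 1 is also amended to place a glucometer reading before the drink.
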